Current practice/treatment in local hospital (IVIG +Rituximab) and existing side effects

IVIG and rituximab combination therapy has not been used in local hospitals for the treatment of pemphigus. This is a pilot study in Hong Kong comparing the use of combination therapy with IVIG and Rituximab versus rituximab alone in the treatment of pemphigus. Ahmad *et al.*⁸ found that combination therapy with IVIG and rituximab in 10 patients with pemphigus with contraindications to systemic corticosteroid resulted in long-term sustained remission (> 6 years). Of note there were lack of adverse events, no infections, deaths or hospitalisations.

Criteria:

Ages Eligible for study : 18 years to 70 years (Adult, Older Adult), by the day of signing informed consent

Sexes Eligible for study : All

Inclusion Criteria:

- Written informed consent obtained from patient
- Ages Eligible for Study: 18 years to 70 years (Adult, Older Adult)
- Newly or recently diagnosed (less than 18 months) diagnosed pemphigus vulgaris or pemphigus foliaceus based on clinical features; histological features of acantholysis via skin or mucosal biopsy; and intercellular staining pattern of indirect immunofluorescence or serological detection of DSG 1 or DSG 3 by enzyme-linked immunosorbent assay (ELISA)
- Moderate to severe active disease, as defined by overall PDAI \geq 15 or skin involvement BSA \geq 5%.⁹ [Annex 1]
- Receiving standard-of-care oral prednisolone up to 1.5 mg/kg/day
- Women who are sexually active and not postmenopausal, agreement to remain abstinent or use 2 effective methods of contraception.
- Ability to comply with study protocol as deemed by investigator's assessment

Exclusion criteria:

- Age <18 or >70
- Pregnant women or nursing mother
- Already diagnosed pemphigus patients diagnosed > 18 months
- Non-consenting patients, or patient who cannot be followed up regularly
- Patient with history of serious allergy or anaphylactic reaction to monoclonal antibody treatment
- Severe heart failure (NYHA Class III or IV)
- Unstable angina or myocardial infarction within last 3 months or post-infarction heart failure
- Anaemia (haemoglobin $<10\text{g/dL}$), Neutropenia ($<1000/\text{mm}^3$), Lymphopenia ($<900/\text{mm}^3$), thrombocytopenia ($<100,000/\text{mm}^3$)
- Renal insufficiency eGFR <60
- Liver insufficiency of ALT/AST > 2 times normal limit range
- Positive test results for hepatitis C (HCV) serology at screening
- Blood test positive for HIV

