- Signs of active infection on CXR
- Positive interferon gamma release assay Quantiferon or T.Spot TB test: must be treated with at least 4 weeks post initiation of isoniazid or other TB therapy
- Inherited or acquired severe immunodeficiency
- History of malignancy
- Patient with active severe infection (excluding fungal infections of the nail), which has required antibiotic treatment within 2 week prior to study enrolment
- Infection requiring hospitalisation or intravenous antibiotic treatment within the last 8 weeks prior to enrolment

- Past history of osteomyelitis, or fasciitis, septic arthritis within the last one year
- Patients with drug induced pemphigus. A thorough medication history will be taken to rule out drug induced pemphigus including D-penicillamine, angiotensin-converting enzyme inhibitors, angiotensin receptor blockers and cephalosporins
- Evidence of any new or uncontrolled concomitant disease that in the investigators' judgement would preclude the patients participation
- Patients with history of allergy or adverse events to IVIG or rituximab treatment¹⁰
- Treatment with intravenous immunoglobulins, plasmaphoresis within the last 8 weeks prior to randomization
- Previous treatment with rituximab or any monoclonal antibody inducing profound lymphopenia
- Treatment with live or attenuated vaccine within the last 28 days prior to randomization

Admission and follow up:

- All infusions will be performed as in-patient procedure of prospective hospital and all patients are to be follow up monthly at out-patient of the prospective Queen Mary Hospital dermatology out-patient clinic
- Patients will be followed up monthly for the first 6 months, then followed up for every 3 months up to 4 years starting from baseline visit

Outcome measures:

Patients' serum will also be taken for desmoglein antibodies and levels will be charted and independent samples t-test will be used to compare the collected data between the two groups. Homogeneity of the treatment groups at baseline will be analyzed using the Mann–Whitney U test and Wilcoxon signed-rank test for independent and dependent variables. The Kaplan-Meier method will be used to estimate the likelihood of reaching the endpoint of relapses or flares within the drug infusing period based on the intention-to-treat population, defined as all patients who has received at least one dose of study medication. The log-rank test will be used to compare time-to-event curves between treatment groups.

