Statistical analysis of results will be done with IBM SPSS statistic program version 25. All tests of significance are two-tailed, and a P value of < 0.05 is considered to indicate statistical significance.

Primary outcome:

- 1) Percentage of participants who achieve relapse-free complete remission

Secondary Outcomes:

- 2) Time to protocol defined disease flare
- 3) Duration of complete remission, evaluated by the PDAI activity score [Baseline up to end of study]
- 4) Number of protocol defined disease flares
- 5) Time to initial complete remission, evaluated by the PDAI activity score [Baseline up to end of study]
- 6) Change in health-related quality of life as measured by the Dermatology Life Quality Index (DLQI) Score [Time Frame: Baseline, Week 4, 12, 24, 36, 48, 60, 72, 84, 96, 120, 144, 168, 192]
- 7) Occurrence of severe treatment adverse events (grade 3 or 4) based on common terminology criteria for adverse events (CTCAE), or death from any cause
- 8) Blood DSG 1 and 3 levels [Baseline week 0, week 4, 12, 20, 24, 36, 48, 60, 72, 96, 120, 144, 168, 192]
- 9) Blood lymphocyte level (CBC) [Baseline week 0, week 4, 12, 24, 36, 48, 60, 72, 96, 120, 144, 168, 192]
- 10) Blood CD19/20 mean B cell counts percentage [Time Frame: Baseline, week 4, 12, 20, 24, 36, 48, 60, 72, 96, 120, 144, 168, 180, 192]
- 11) Number of rescue therapy given

Baseline investigations prior to commencing therapy

General investigations:

- CBC
- Renal panel
- Liver panel
- Fasting Glucose/HbA1c
- Urine microscopy
- Urine pregnancy test in women of childbearing age
- Serum immunoglobulins for IgA deficiency
- B cell (CD19/20) enumeration

- DSG 1, 3 ELISA

Infective screen:

- HepBs Ag, Anti-HBs Ab, anti-HepBc total antibodies
- Anti-HCV IgG
- Anti HIV 1 and 2 (if indicated)
- CXR
- Interferon-gamma release assays

Patients who have positive IGRA test results

As Tuberculosis (TB) is endemic in Southeast Asia, should Interferon-gamma release assays result be positive, the patient will be reviewed by infectious diseases specialist and need treatment of latent TB treatment prior to starting Rituximab. Patients will need to have completed at least 4 weeks of isoniazid or treatment with other TB medications, before commencement of the study.

Patients who are HepBs Ag positive, or HepBs Ag negative and anti-HepBc Ab – positive

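### Desmoglein antibody levels are compared by a plain t-test although entry admits patients negative for DSG 1, DSG 3 or both; this dilutes the comparison and costs power

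*Protocol*

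**What the plan says.** **Entry.** Protocol, Inclusion Criteria, accepts "diagnosed pemphigus vulgaris or pemphigus foliaceus based on clinical features", with acantholysis on biopsy and "intercellular staining pattern of indirect immunofluorescence or serological detection of DSG 1 or DSG 3 by enzyme-linked immunosorbent assay (ELISA"). The clause "serological detection of DSG 1 or DSG 3 by enzyme-linked immunosorbent assay (ELISA") is thus only part of the last element, which has three alternatives: the immunofluorescence pattern, DSG 1 by ELISA, or DSG 3 by ELISA. Any one is enough.

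**Outcome.** Secondary Outcomes, item 8, is "Blood DSG 1 and 3 levels [Baseline week 0, week 4, 12, 20, 24, 36, 48, 60, 72, 96, 120, 144, 168, 192"]. It is not limited to patients positive for the antigen concerned.

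**Test.** Under Outcome measures, "levels will be charted and independent samples t-test will be used to compare the collected data between the two groups". No transformation, baseline covariate or subset is named for these levels. The general rule is "All tests of significance are two-tailed, and a P value of < 0.05 is considered to indicate statistical significance".

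**Data already collected.** Baseline investigations include the DSG 1 and DSG 3 ELISA, so antigen status before treatment will be known for every patient.

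**Size.** Methods plans about 10 patients per arm. No power, effect size or SD is given for the desmoglein comparison.

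**The concern.** The entry rule and the stated test fit poorly together. A patient who qualifies through one antibody may have no measurable level of the other, and a patient who qualifies on immunofluorescence may have neither. For that antigen the patient has nothing to lose under either treatment. Kept in a comparison of mean levels, such patients pull the two arm means together. They also add spread, because low negative values sit beside positive titres.

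Separately, antibody titres are usually right-skewed. A mean on the measured scale then depends heavily on a few high values, which costs power even if every patient is positive.

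At stake is a secondary biomarker comparison in about 20 patients. A real difference in antibody decline could be missed. Nothing here touches the primary outcome.

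**Working it through.** The protocol gives no power or effect size for this outcome, so there is no figure of its own to reproduce. From the protocol come 10 per arm, 1:1 allocation, two-sided 0.05 and the t-test. Everything else below is an assumption.

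**Step 1: dilution alone, closed form.** Let f be the share positive for the antigen, d the arm difference among positives in SD units, and m the gap between control-arm positives and the negative level, also in SD units. Negatives are taken as constant.

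- Mean difference in all patients: f·d
- Variance, control arm: f + f(1−f)m²
- Variance, treated arm: f + f(1−f)(m−d)²
- Power ≈ Φ(δ·√(n/2) − 1.96), where δ is the difference divided by the root of the average variance

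With no negatives, d = 1.25 and n = 10: 1.25·√5 = 2.795, less 1.96 gives 0.835, power 0.80.

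With f = 0.7, d = 1.25, m = 2:

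- Difference: 0.7 × 1.25 = 0.875
- Variances: 0.7 + 0.21 × 4 = 1.54 and 0.7 + 0.21 × 0.5625 = 0.818; average 1.179, root 1.086
- δ = 0.875/1.086 = 0.806; power = Φ(0.806 × 2.236 − 1.96) = 0.44
- Positives only, 7 per arm: Φ(1.25 × √3.5 − 1.96) = 0.65

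| Share positive | All patients | Positives only | Ratio |
|---|---|---|---|
| 0.9 | 0.67 | 0.76 | 0.88 |
| 0.7 | 0.44 | 0.65 | 0.68 |
| 0.5 | 0.27 | 0.51 | 0.54 |

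Dropping the negatives raises power although it shrinks the sample.

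**Step 2: dilution and skewness together, by simulation.** Assumed: 10 per arm; positives lognormal, median 100 at baseline, 50 at follow-up in one arm and 50/3 in the other (a 3-fold difference); log-SD 0.8; baseline correlation 0.5; negatives stable at median 3 with log-SD 0.5.

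| Share negative | Plain t-test, raw scale, all | Log scale, baseline-adjusted, positives only |
|---|---|---|
| 10% | 54% | 86% |
| 30% | 31% | 70% |
| 50% | 17% | 50% |

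Separate runs of the same model agree to within about 3 percentage points. With log-SD 1.0 and 30% negative, the pair is about 21% v 54%.

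**Step 3: where the gain comes from, at 30% negative and log-SD 0.8.**

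| Analysis | Power | Gain |
|---|---|---|
| Raw, all patients | 31% | |
| Raw, positives only | 48% | +17 |
| Log, positives only | 63% | +15 |
| Log, baseline-adjusted, positives only | 70% | +7 |

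The negatives account for 17 of the 39 points. Logging without the restriction gives 24%, below the plain test, because the log scale widens the gap between negatives and positives. That is not universal: in a second model, with half negative, a 4-fold difference and log-SD 1.0, logging in all patients raises power from 16% to 27%. It still falls short of 45% for log scale in positives.

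**Step 4: type I error.** With no true difference, rejection is about 3 to 6% for all methods.

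**The case against.** **The text does not say raw scale or all patients.** This is right. The protocol is silent on scale, subset, time point and level versus change. A t-test on log ratios would still be an independent samples t-test, and a statistical analysis plan, not available here, could set these details. What stands is that the protocol commits to a specific test of levels between the two groups. Its plain reading is measured values in the groups as randomised, and its own entry rule makes that a weak choice.

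**A reader might infer that entry requires a desmoglein antibody.** It does not, because immunofluorescence is an alternative. This makes dilution more likely, since a patient may be negative for both antigens.

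**A reader might infer that negatives swamp the comparison and by themselves halve its power.** The protocol gives no share of negatives, SD or effect from which to derive that. On a fixed raw scale, negatives cut power to about 0.65 of the positives-only value at 30% negative (31/48). They reach about half only when about half the patients are negative (16% v 31%). Larger ratios add in the separate gains from the log scale and baseline adjustment.

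**A reader might see a contradiction with the rank test used for baseline variables.** That test serves a different purpose, baseline homogeneity. In the model of Step 2, a rank test in all patients has less power than the raw t-test (24% v 33% in one run).

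**The improvement may not suffice.** Also fair. At 30% negative and log-SD 0.8, a 2-fold difference gives about 15% v 31%, and a 1.5-fold difference about 8% v 15%.

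**Chance imbalance in negatives between arms is not bias.** Correct; the t-test's variance already reflects it.

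**Conclusion.** The point holds as one of efficiency. The entry rule allows patients negative for a given antigen, the protocol fixes a plain t-test on levels, and no restriction, transformation or baseline adjustment is stated. In every setting run, the log-scale analysis in baseline-positives had at least as much power as the plain test.

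The size is conditional. Under the Step 2 assumptions the gain is 32 to 39 points for 10 to 50% negative. Over a wider set of assumed effects and SDs, comparing the plain test with an unadjusted log-scale t-test in positives, the power ratio runs from 0.99 (10% negative, large effect) down to 0.25 (70% negative). No single figure for the loss should be quoted.

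Validity is not in question, and this is one secondary biomarker in a self-described pilot. It is a cheap improvement, not a flaw that threatens the trial's conclusions.

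**What to change.** Add one or two sentences under Outcome measures or in the analysis plan. DSG 1 and DSG 3 are each analysed in patients positive for that antigen at week 0. The log level is the response and the log baseline level the covariate, and the result is reported as a geometric mean ratio with its confidence interval. Antigen-negative patients are listed descriptively. State the assay's positivity cut-off and the time point of the comparison in advance.

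The restriction and the log scale should be adopted together, since logging alone can lower power. The subset is defined by a pre-treatment value, so the randomised comparison is kept, and the baseline ELISA is already required, so no new data are needed.

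The cost is a smaller set per antigen (about 7 per arm if 30% are negative). Antibodies that newly arise in baseline-negative patients would be described only, without inference.

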Cost effectiveness is an important issue and while combination of IVIG and rituximab has been advocated, the cost of such treatment is substantial and whether it poses any benefit over rituximab alone, or with other more conventional immunosuppressive agents, has not been established. Both treatment approaches have been previously published in high impact journals.^{3,5} In this study, we aim to evaluate the efficacy and safety of early use of rituximab with or without IVIG in patients with moderate to severe pemphigus using protocols that were similar to those previously published. Apart from complete remission and adverse effects, we will also aim to measure the impact of health care economics and in doing so, assess the cost and benefits of both treatment arms.

Hypothesis:

IVIg in combination with Rituximab is more superior than Rituximab alone in the treatment of moderate to severe pemphigus.

Methods:

Prospective multi-centre, randomised open-label trial

Patients will be randomised to two treatment arms: Rituximab alone or Rituximab + IVIG

Aim to recruit ~10 patients per arm (20 patients in total)

Patients will be reviewed monthly for the first 6 months then 3 monthly in clinic thereafter, follow up will be up to 4 years.

When patient enrolment is confirmed and written consent is obtained, the investigator will open the envelop sequentially and patient will receive the treatment plan stated on the allocation slip. Patient will be randomised to either rituximab arm or rituximab and IVIG arm. The random allocation sequence will be generated using computer-generated random numbers. Randomisation will be to the two arms of the trial in 1:1 ratio. The allocation sequence will be printed on paper slip. A non-study related research assistant will put the slips in to sequentially numbered, opaque, sealed envelopes.

Arm 1 (Rituximab alone arm):

- Rituximab infusion 375mg/m² body surface area (BSA) weekly for 4 weeks from baseline
- Rituximab infusion 375mg/m² BSA weekly for 4 weeks at week 24
- Rituximab infusion 375mg/m² BSA weekly for 4 weeks at week 52
- A total of 12 doses of rituximab will be given in 55 weeks
- If a patient relapses after initial rituximab infusion, further rituximab infusion 375mg/m² BSA weekly for 4 weeks can be given at time of relapse/or if patient fails to achieve complete remission 2 months from last dose of rituximab.

Week 0, 1, 2, 3	Rituximab (375mg/m ²)
Week 24, 25, 26, 27	Rituximab (375mg/m ²)

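### The desmoglein comparison is a plain two-sample t-test that leaves out the week 0 level already being collected; adjusting for it costs almost nothing and probably gains precision

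*Protocol*

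**What the plan says.** Under Outcome measures, the protocol has desmoglein levels charted and states that an "independent samples t-test will be used to compare the collected data between the two groups". No other test is named for this outcome.

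Secondary Outcomes, item 8, gives the schedule: "Blood DSG 1 and 3 levels [Baseline week 0, week 4, 12, 20, 24, 36, 48, 60, 72, 96, 120, 144, 168, 192". That is one baseline and 13 later measurements for each of two antibodies. The DSG 1, 3 ELISA is also on the list of baseline investigations before therapy. No visit is singled out for the comparison.

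Item 8 speaks of levels. Item 6, by contrast, is worded as a change: "Change in health-related quality of life as measured by the Dermatology Life Quality Index (DLQI) Score".

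Baseline enters the statistical text only here: "Homogeneity of the treatment groups at baseline will be analyzed using the Mann–Whitney U test and Wilcoxon signed-rank test", the sentence continuing with a reference to independent and dependent variables.

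The Methods section aims for about 10 patients per arm, and says "Randomisation will be to the two arms of the trial in 1:1 ratio". Testing is two-sided at 0.05.

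**The concern.** A two-sample t-test on follow-up levels discards what the week 0 level says about each patient's later level. With about 10 per arm, two things follow.

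- **Chance imbalance is not corrected.** A baseline difference between the arms carries into the follow-up difference in proportion to the baseline-to-follow-up slope.
- **Precision may be lost.** Variation between patients that baseline would explain stays in the error term.

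The homogeneity test does not help, because testing for imbalance does not adjust the comparison. One of the two tests named for it, the signed-rank test, is a paired test and cannot compare two independent arms.

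At stake is how much a small pilot can say about an antibody outcome. The protocol itself fixes the t-test, so this is not a detail left to a later analysis plan.

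**Working it through.** The protocol gives no SD, effect size or power for this outcome, so there is no stated figure to reproduce.

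**Inputs from the protocol:** n = 10 per arm, N = 20, 1:1 allocation, two-sided 0.05.

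**Assumptions:** normal data, equal SDs at baseline and follow-up, and a baseline-to-follow-up correlation r that the protocol does not give, shown from 0 to 0.7. Differences are in SD units.

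**1. The t-test as planned.** On 18 degrees of freedom it has 56% power for a difference of 1 SD. It reaches 80% power at 1.325 SD.

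**2. Variance under ANCOVA.** Allowing for estimation of the slope, the expected variance ratio of ANCOVA to the t-test is

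(1 − r²) × [1 + 1/(N − 4)] = (1 − r²) × (1 + 1/16) = (1 − r²) × 1.0625.

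A t-test on change from baseline would have variance ratio 2(1 − r) to the t-test on levels. Power in the last column is at 1.325 SD, from 40,000 simulated trials per setting; the t-test on levels has 80% there.

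| r | ANCOVA / t-test variance | Change score / t-test variance | ANCOVA power |
|---|---|---|---|
| 0 | 1 × 1.0625 = 1.06 | 2.00 | 78% |
| 0.3 | 0.91 × 1.0625 = 0.97 | 1.40 | 81% |
| 0.5 | 0.75 × 1.0625 = 0.80 | 1.00 | 88% |
| 0.7 | 0.51 × 1.0625 = 0.54 | 0.60 | 97% |

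Break-even is where (1 − r²) × 1.0625 = 1, so r = √(1 − 1/1.0625) = 0.243. Simulated variance ratios agreed with the formula. Both tests rejected in about 5% of null trials.

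**3. Equivalent sample size.** Dividing 20 by the variance ratio, ANCOVA is worth a t-test on 20/0.797 ≈ 25 patients at r = 0.5 and on 20/0.542 ≈ 37 at r = 0.7. At r = 0 it is worth 20/1.0625 ≈ 19.

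**4. Chance imbalance.** The standard error of the baseline difference is √(2/10) = 0.447 SD. The chance of a difference of at least 0.5 SD in either direction, on a given antibody, is 2 × [1 − Φ(0.5/0.447)] = 2 × [1 − Φ(1.118)] = 26%. With equal SDs the slope equals r, so a 0.5 SD imbalance shifts the expected follow-up difference by 0.5 × r: 0.15, 0.25 and 0.35 SD at r = 0.3, 0.5 and 0.7. Among simulated null trials with an imbalance that large, the t-test rejected in roughly 7%, 9% and 13%; ANCOVA stayed near 5%.

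**5. Number of comparisons.** With no visit named, 13 later visits × 2 antibodies allow up to 26 t-tests at 0.05.

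**The case against.** The strongest reply is that nothing here is an error. The t-test is valid, the outcome is a laboratory secondary in a pilot of about 20 patients, and no power claim is attached to it. The gain rests wholly on r, which the protocol does not give. Both arms receive rituximab, with further courses possible at relapse, so the week 0 level may predict late levels poorly. Below r of about 0.24 ANCOVA loses slightly. All of this stands, and it is why the point is one of efficiency with a gain that is likely but not assured.

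Second, the data to be compared are not defined, so a change score might be meant, and week 0 would then be used. The contrast between item 8 and item 6 points the other way, but it is an inference from labels. The conclusion survives either reading: ANCOVA has the smaller variance at every r in the table, though at r = 0.7 the gap is small (0.54 against 0.60).

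Third, the baseline sentence ends with "Wilcoxon signed-rank test for independent and dependent variables" and could be read respectively, with the signed-rank test reserved for paired data. That is possible, but the sentence's stated subject is homogeneity of the arms at baseline, and a within-arm paired test would still not adjust the comparison between arms. This is a side issue to the main point.

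Fourth, naming a single visit is a multiplicity decision and goes beyond baseline adjustment; a repeated-measures model is an alternative. That is fair. One named visit is proposed because it is simple and closes the choice among up to 26 tests. The case for using week 0 does not depend on it.

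**Conclusion.** The concern holds. On its natural reading, the protocol fixes an analysis of DSG 1 and DSG 3 that ignores a baseline value planned for every patient. With 20 patients, adjustment costs at most about 6% in variance if baseline is uninformative, and saves about 20% at r = 0.5 and 46% at r = 0.7. About one trial in four would show a baseline difference of 0.5 SD or more on a given antibody, which the t-test would leave in the result.

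These sizes rest on the assumed r, on normality and on equal SDs. Antibody levels may be skewed, and eligibility does not require both antibodies to be detectable, so the figures are illustrative. The change should be made because the cost is small and known; it improves a secondary outcome and corrects no bias.

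**What to change.** - Replace the t-test by ANCOVA, fitted separately for DSG 1 and DSG 3, with arm and the week 0 level as terms.
- Apply it at one post-baseline visit chosen in advance from the item 8 schedule. Report the adjusted difference with its 95% confidence interval, and the other visits descriptively.
- State the scale in advance. If levels are expected to be skewed, use logs with a stated rule for zero or undetectable values.
- Summarise baseline by arm descriptively, and drop the homogeneity tests, including the signed-rank test.

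The cost is a change of wording, one degree of freedom and, if logs are used, the rule for undetectable values. The week 0 sample is already planned and the named software (SPSS) fits the model.

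### The desmoglein t-test is applied to serial measurements (two antigens, 13 post-baseline visits) without fixing the visit or the patient-level value to be compared

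*Protocol*

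**What the plan says.** The Outcome measures section of the protocol says that serum desmoglein antibody levels will be charted and that an "independent samples t-test will be used to compare the collected data between the two groups". It names no visit, change score, summary measure or longitudinal model for this comparison.

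The statistical paragraph that follows sets the decision rule: "All tests of significance are two-tailed, and a P value of < 0.05 is considered to indicate statistical significance". No adjustment for multiple tests is mentioned.

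Secondary Outcomes, item 8, gives the schedule: "Blood DSG 1 and 3 levels [Baseline week 0, week 4, 12, 20, 24, 36, 48, 60, 72, 96, 120, 144, 168, 192". That is week 0 and 13 later weeks, for two antigens.

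The Methods section gives the size and allocation: "Aim to recruit ~10 patients per arm (20 patients in total" and "Randomisation will be to the two arms of the trial in 1:1 ratio". The section on current practice in the local hospital describes the trial as a pilot: "This is a pilot study in Hong Kong comparing the use of combination therapy with IVIG and Rituximab versus rituximab alone".

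**The concern.** An independent-samples t-test assumes that every value in the comparison comes from a different, unrelated unit. The desmoglein data are repeated values from about 20 patients followed to week 192. The sentence does not say how the test is to be fitted to such data, and two obvious ways of following it lead to trouble. One test per visit gives many tests with no lead among them. One test on all visits together counts each patient up to 13 times.

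The protocol's rationale for adding IVIG refers to serological remission and to suppression of pathogenic autoantibodies, and desmoglein titres measure this directly. With about 10 patients per arm, a chance difference at some visit could be reported as mechanistic support for the combination, whose cost the protocol itself calls substantial. The choice of test is already made in the protocol. A later analysis plan would therefore either inherit the gap or, if it used a longitudinal model, depart from the sentence.

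**Working it through.** The protocol states no family-wise error rate and no power calculation, so there is no figure of its own to reproduce.

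**Inputs from the protocol**
- Antigens: 2. Post-baseline visits: weeks 4, 12, 20, 24, 36, 48, 60, 72, 96, 120, 144, 168, 192 = 13.
- Possible visit-level comparisons: 2 × 13 = 26.
- Significance level: 0.05 two-sided for each test. Arms: 10 and 10.

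**Assumptions (not in the protocol)**
- Normal data (for example after a log transformation), complete follow-up, no true difference between arms.
- Correlation between visits of one patient: 0.3 to 0.9 if equal for all pairs of visits, or autoregressive with 0.7 to 0.95 between neighbouring visits.
- Correlation between the two antigens: 0 to 0.8.

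**Reading A: one t-test per visit and antigen**

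Expected number of false positives: 26 × 0.05 = 1.3, whatever the correlation.

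If all tests are independent, the chance of at least one is 1 − 0.95^26 = 0.736. For one antigen alone it is 1 − 0.95^13 = 0.487.

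With correlated visits it was simulated (10,000 trials per setting). Chance of at least one P < 0.05 among 26, equal correlation between visits:

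| Within-patient correlation | Antigens uncorrelated | Antigens correlated 0.8 |
|---|---|---|
| 0.3 | 67% | 58% |
| 0.5 | 57% | 50% |
| 0.7 | 43% | 36% |
| 0.8 | 36% | 29% |
| 0.9 | 27% | 22% |

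The autoregressive settings lie within the same band. With uncorrelated antigens, for example, they give 61% at 0.7 and 42% at 0.9. Allowing for simulation error across repeated runs, the range is about 21-68%.

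**Reading B: all visits pooled as if independent, one antigen**

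With equal correlation r over m = 13 visits, the true variance of an arm mean exceeds the one that the test assumes by a factor of about 1 + (m − 1)r. The type I error is then about 2 × [1 − Φ(1.96 / √(1 + 12r))].
- r = 0.3: √4.6 = 2.145; 1.96 / 2.145 = 0.914; error about 36%.
- r = 0.9: √11.8 = 3.435; 1.96 / 3.435 = 0.571; error about 57%.

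Simulation gives slightly more at the upper end, because the pooled standard deviation is also underestimated. Over all settings the range is about 35-59%.

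**Reading C: one prespecified value per patient**

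A t-test on each patient's post-baseline mean, 10 against 10, had a simulated type I error of about 5% in every setting (roughly 4-6%). With one such test per antigen, the chance of at least one false positive is 1 − 0.95² = 9.75% if the antigens are independent, and 10% at most under any dependence.

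A and B move in opposite directions. Strong within-patient correlation lowers the visit-by-visit figure and raises the pooled one, so no correlation in the range rescues both.

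**The case against.** The strongest reply is that the protocol prescribes neither Reading A nor Reading B. It says only that the data are compared by a t-test, and Reading C, which is valid, fits those words. The time point or summary could be settled in an analysis plan that is not shown. This stands in part. Visit-by-visit testing and pooling are natural readings, not stated rules, and it would be wrong to say that every way of following the sentence fails. What remains is that the protocol fixes the test, lists 26 possible post-baseline comparisons, and names no unit that would make the test fit. Even a single test at one visit holds 5% only if that visit is chosen before the data are seen.

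A second reply is that P < 0.05 is a per-test rule, and under Reading A each test does keep its 5%. That is correct. The 21-74% is the chance that at least one of the 26 is significant. It matters only if such a result is put forward as evidence, which nothing in the text prevents.

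A reader might also infer that a spurious significant result is more likely than not. The documents do not support this. Under Reading A the chance passes 50% only up to moderate correlation (about 0.5-0.6 if equal between visits, about 0.7-0.8 if autoregressive). It falls well below that with strong correlation, which is plausible for repeated antibody levels in one patient. The protocol gives no correlation from which to decide.

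Finally, desmoglein level is item 8 in the outcome list of a pilot study. Strict family-wise control over such a biomarker is not obligatory, and none is asked for here.

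**Conclusion.** The point holds in a limited form. The protocol applies an independent-samples t-test at 0.05 to serial desmoglein data without saying which value per patient is compared. The false-positive risk is about 74% for any of 26 visit-level tests if independent, and roughly 21-68% over the assumed correlations. It is about 35-59% for one antigen if visits are pooled. With one prespecified value per patient it is about 5%. In every setting tried, the first two are at least four times the nominal level.

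The exact figures rest on assumed correlations, normal data and full follow-up of 10 patients per arm, so they show the order of the problem and do not predict this trial. The point concerns the credibility of a secondary serological claim. It leaves the primary outcome and its conclusion untouched. The sentence should be corrected, but the trial does not depend on it.

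**What to change.** Replace the t-test sentence in Outcome measures by one prespecified comparison per antigen with the patient as the unit. Either of these would do:

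- a t-test on one summary value per patient, for example the mean log level over the post-baseline visits to a stated week, with a rule for missed visits; or
- a repeated-measures mixed model over the scheduled visits, with one stated contrast between arms.

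Show the visit-by-visit curves for both antigens descriptively, without P values.

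This is a change of wording only: no extra samples, visits or patients. The downside is small: P values for single visits can no longer be quoted.
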